5.2.3 Hypotheses to be accepted or rejected by statistical data from the study

The primary hypothesis is that the time period from index therapy to release for oral food intake (in upper GI tract use) or endoscopic release for stoma relocation (in lower GI tract use) will be superior to historic controls from literature reporting standard management of therapy without use of EVAC therapies.

A Statistical Analysis Plan (SAP) will be prepared prior to start of data analysis detailing the statistical analysis methods which will be used.

5.3 Scientific justification and clinical relevance for effect sizes, non-inferiority margins or equivalence limits

This observational study will provide information on "real world" use and practice in treatment of both upper and lower GI tract perforations and anastomotic insufficiencies using the Suprasorb[®] CNP endo system in a routine clinical care setting.

The indication for this treatment is decided in acute clinical situations needing urgent treatment, thus, a controlled clinical trial setting will be impractical and may lead to a larger selection bias compared to a study which reports observation of routine clinical care without pre-defined study procedures and interventions.

The study will only be performed in study sites which are trained for the use of the Suprasorb[®] CNP endo system treatment in routine clinical care and generally experienced in use of EVT for treatment of upper or

lower GI tract perforations and anastomotic insufficiencies. Thus, comparability in selection of patients, decision on indication and procedures performed can be presumed.

5.4 Risks and anticipated adverse device effects that are to be assessed

The investigational device is a marketed, CE-certified product, which will be used within its intendent purpose. Rate of defect treatment complications (during index defect treatment and in follow-up treatments) and rate of SAEs related to defect treatment will be assessed. The term "defect treatment related" represents not only device-related but in total procedure-related AEs of special interest and SAEs. Non-serious AEs which are not classified as "of special interest" will not be assessed.

6. Design of the clinical study

6.1 General

6.1.1 Study design

This PMCF study designed as non-interventional, observational, prospective, multicentre study in a routine clinical care setting using a marketed medical device in line with the corresponding IFU in the intended patient population.

The routine clinical care of study patients is in no way influenced by their participation in this study. All clinical procedures and therapies are based on individual decisions of the treating physician following current applicable medical guidelines and local policy, not pre-defined in the study protocol. Thus, this clinical study is purely observational.

Patients will be screened at study sites, which have expertise in treatment of oesophageal and / or intestinal defects and are trained for the use of Suprasorb[®] CNP endo treatment.

[figure not shown]
Patients will be enrolled in this non-interventional study if an indication for Suprasorb[®] CNP endo treatment was defined by the treating physician based on routine clinical care decisions, all inclusion and no exclusion criteria are met and written consent is given to use and process their routine clinical data according to data privacy standards.

In most cases, enrolment into the study will take place after Suprasorb[®] CNP endo treatment related to the fact that the treatment decision for such patients is often made in a medically acute situation. A screening form will be used by the study site staff to document some anonymised data of all potentially eligible patients together with a reason if not participating in the study to control selection bias and to maintain prospective data generation.

Patients will be diagnosed and evaluated for eligibility in routine clinical care by expert centres in the indication of interest and enrolled competitively by all authorised study sites without pre-defined quota for individual study sites.

The study protocol does not define specific study procedures for patients enrolled. Therapies and procedures during the course of this study will be performed according to the decision of the treating physician based on current applicable medical guidelines and on local policy in clinical routine care. This includes the prescription and the use of the device of interest and possible measures at enrolment and in follow-up. All devices will be used according to the corresponding IFU, only. The only study-specific obligation within this observational study is to document pre-defined medical and procedural data if available in routine clinical care in the electronic CRF (eCRF) at a level of data quality following international standards on clinical studies.

Flowchart

6.1.2 Measures to minimize or avoid bias

The study site will document all consecutive patients, for whom treatment of acute oesophageal or intestinal defects using Suprasorb[®] CNP endo treatment is clinically indicated. If a potentially eligible patient refuses to consent participation in the study or other reasons for non-participation are existing, the patients' minimum of medical data (age, sex, indication for treatment of interest) will be documented in a Screening Log located at the study site for potential review e.g. by clinical monitors of the CRO to check for potential selection bias. The data in the Screening Log will not be processed centrally.

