6.1.3 Endpoints of the study

6.1.3.1 Primary endpoint

Time period in days from index use of Suprasorb[®] CNP endo to release for oral food intake (in upper GI tract use) or endoscopic release for stoma relocation (in lower GI tract use).

In case of lower GI tract use and no stoma present, time period to release for oral food intake is the relevant endpoint.

6.1.3.2 Secondary endpoints

- 1. Number of SAEs related to defect treatment within total observation period.
- 2. Number of nights in hospital for therapy of index defect.
- 3. Number of nights at the ICU during hospital stay for therapy of index defect.

Nights at an intermediate care unit (IMC) will not count for this secondary endpoint.

SAEs will be adjudicated by an independent Clinical Event Committee (CEC) according to standard definitions. Wherever reasonable, endpoints will be normalised to one year of follow-up to adapt results to varying follow-up periods.

"Index defect" describes for each study patient the defect(s) which lead to the clinical indication of treatment with Suprasorb[®] CNP endo system according to IFU and medical guidelines as defined in 6.3.1.

"Index therapy" describes for each study patient the first use of Suprasorb[®] CNP endo for therapy of the index defect.

6.1.4 Methods and timing for assessing, recording, and analysing variables

Only data which can be obtained from routine clinical care files of the patients will be recorded. Data of routine clinical care visit after study enrolment will be reported in the e-CRF. Data will be derived from clinical records and findings, radiological assessments, observations or other sources (e.g. hospital records, clinical and office charts, electronic patient records, laboratory notes).

Within this observational study timing of measures and clinical data to be reported are determined by routine clinical care in line with applicable medical guidelines and local policies. The study protocol just defines some procedural recommendations.

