6.1.6 Any procedures for the replacement of subjects

No study-specific intervention is defined within this observational study which is only following routine clinical care.

Patients' written informed consent to use and process their routine clinical care data according to data privacy standards will be obtained prior to documentation of any patients' data in the e-CRF. It is expected that in the majority of patients written informed consent to use and process data (enrolment) is provided after index therapy.

The principle for analysis of study data is intention to treat without restrictions to any subsequent course of follow-up.

Thus, no necessity of any procedures for the replacement of patients is foreseeable.

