6.4 Procedures

6.4.1 Study-related procedures

No study-specific procedures are defined in this protocol and will be performed during this observational study but routine clinical care procedures according to applicable medical guidelines, IFU of the devices used and local policy.

"**Enrolment**" in this observational study means the patient is giving informed consent for use of personal medical data, i.e. the legal prerequisite for being part of this clinical observation. Thus, "**date of enrolment**" is the date of the signature on informed consent. In this purely observational study consent for use of data might be given after index treatment because this treatment is performed in routine clinical care without any studyspecific requirements or definitions and might be performed in an acute setting.

"**Baseline visit**" in this observational study is not a specific personal visit of the patient at the study site but a basket to document all relevant data known at baseline. Thus, medical data reported at baseline visit might represent patient's status even before enrolment, e.g. data on medical history. Use of these data is covered by the informed consent given by the patient.

Due to the acute defects in focus and the corresponding indication of invasive treatment in this purely observational study, "date of enrolment" (=date of informed consent for use of personal medical data) might therefore be after "date of index treatment".

"Start of observation" with respect to the objectives and endpoints of this study is the time point of the index treatment.

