6.4.3 Screening and baseline/enrolment visit (day 1 of observation)

Patients will be screened and enrolled by contracted study sites only, i.e. expert centres. Screening of potentially eligible patients will be performed within routine clinical care. Check for eligibility according to in- and exclusion criteria will be performed using routine clinical care data.

Potentially eligible patients will be informed about the use of their medical data in the study. The patient will be given sufficient time to consider the implications of data use before deciding whether to consent. Participation in this study means following clinical routine care procedures, but allowing for documentation of medical data in a central web-based data base (e-CRF). If the patient is willing to agree, the informed consent form for data use will be provided for signature. As soon as signed informed consent is available, the patient has been enrolled into the study.

Informed consent for use of personal medical data will often be given after the date of index treatment because the treatment is performed in routine clinical care. The fact of enrolment and the enrolment date will in any way be documented within the baseline visit. After signing the consent, patients are checked for eligibility according to in- and exclusion criteria by the participating sites consecutively to minimise selection bias. Study relevant data will be reported in the e-CRF. The e-CRF system will automatically display the patient ID as consecutive number across all participating study sites, i.e. without reference to the recruiting site.

The following data items will be documented of each participating patient at enrolment:

- Demographic data
- Patient's physical status
- Medical history
- Relevant concomitant medication and diseases

Data on the entire clinical stay for treatment of the index defect will be documented.

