6.4.4 Treatment of the index defect

The decision of treatment of the index defect lies with the treating physician in routine clinical care. Indication as well as initiation of treatment should follow applicable medical guidelines, local clinical care policy and the IFUs of the devices used.

Initiation of treatment might start as routine clinical care procedure before enrolment into the study (i.e. informed consent of the patient) but data can be entered into the e-CRF after signed informed consent is available (i.e. after enrolment), only.

- Primary EV therapy is defined as the utilisation of EVT as first-line therapy for perforation or leak.
- **Rescue EV therapy** is defined as EVT placement following failure of definitive surgical repair for a perforation or leak.
- **Defect closure following EVT placement** is defined as 1) no evidence of continued leak under direct endoscopic visualization and 2) a negative oesophagram following discontinuation of EVT therapy.

Data regarding index defect, related therapy and outcome following EVT placement will be documented in the e-CRF at the Index-treatment visit.

The following data items will be documented of each participating patient at the index-treatment visit:

- Data of index treatment and related therapy (defect size, type and location of perforation, pre-existing pathology, ASA-classification, Perforation Severity Score (PSS), primary or rescue EVT application, type of endo-sponge placement, type of surgical repair, time to placement of EVT following diagnosis, number of EVT changes, number of days between EVT changes, total length of EVT therapy, relevant laboratory parameters)
- Outcome of index treatment (including 30-day mortality, closure interventions following treatment of index defect, hospital length of stay (LOS), ICU LOS, EVT therapy-specific findings (e.g. migration, dislodgement, erosion), time to oral diet initiation / endoscopic release for stoma relocation following successful defect closure).

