Patients undergoing the procedures of interest in this study will often be in a clinical situation requiring immediate therapy without any delay. In addition, it is expected that potential study patients might not be able to give informed consent on the use of their personal data at the time of physician's decision on the primary intervention procedure of interest. Since this clinical study is purely observational, all therapies used are decided individually by the treating physician in routine clinical care in line with medical guidelines and the IFUs of the devices used but not pre-defined in the study protocol. Thus, informed consent for use of personal data will be given subsequent to the primary intervention procedure of interest but before any data transfer to the e-CRF.

Should there be any modifications to the protocol, such that this would directly affect the patient's consent for transfer, processing and use of their personal medical data in the study, an addendum to the informed consent form specifying the modification must be compiled and the active patients must agree to sign this addendum indicating that they also agree to the modifications within the study.

A signed copy of the patient's informed consent form must be maintained in the study file on site, a copy of the signed informed consent form must be provided to the study patient. The patient's permanent medical records should indicate the patient's study participation.

14. Adverse events, adverse device effects and device deficiencies

SAEs will be documented following ISO 14155:2020 and reported in accordance with applicable national standards. Since the study is observational, all therapies and procedures represent routine clinical care in line with applicable medical guidelines, market authorisations and corresponding IFUs. Since no risks or benefits compared to routine clinical care will be added, the rate of non-serious AEs will be identical to routine clinical care. Thus, non-serious AEs will not be documented within this study but AEs of special interest (AEoSI), only (refer to section 14.1).

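### Patients who die or stay incapable before consenting enter no endpoint, and the screening log meant to show this loss is kept from central use

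*Protocol*

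**What the plan says.** **Time zero.** Section 6.4.1 says that the start of observation "with respect to the objectives and endpoints of this study is the time point of the index treatment". The primary endpoint in 6.1.3.1 is the "Time period in days from index use of Suprasorb" CNP endo to release for oral food intake or for stoma relocation.

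**Entry.** Signed consent is inclusion criterion I4 (6.3.1) and must precede any e-CRF entry (6.1.6, 13). Section 6.1.6 adds: "It is expected that in the majority of patients written informed consent to use and process data (enrolment) is provided after index therapy". Section 13 says that "informed consent for use of personal data will be given subsequent to the primary intervention procedure of interest". Sections 13 and 15 expect that patients may be unable to consent when treatment is decided, and the text shown describes only the patient's own consent.

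**The safeguard.** Section 6.1.1 provides a screening form for all potentially eligible patients, "together with a reason if not participating in the study to control selection bias and to maintain prospective data generation". Section 6.4.2 gives the log the same purpose. Section 6.1.2 lists its content as age, sex and indication, keeps it at the site for potential review by monitors, and closes: "The data in the Screening Log will not be processed centrally". Section 6.5 plans no routine on-site monitoring.

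**Other places.** Sections 6.4.8 and 8.1 mention pooled site-level details for control of selection bias. Section 6.4.4 records "Outcome of index treatment (including 30-day mortality" among other items. Section 6.1.6 names intention to treat as the analysis principle, and section 7 makes the superiority test against published controls confirmatory.

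**The concern.** A patient can be counted only by surviving, with capacity, from index use to signature, yet the clock runs from index use. Patients lost in between contribute no time at risk, no SAE and no death. They are plausibly among the least likely to be released for food or stoma relocation, so removing them can raise the apparent release rate. There is no concurrent control group that would share the selection.

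Late consent is unavoidable in this setting. What can be avoided is having no study-level record of how many treated patients were lost this way. The protocol names an instrument for that and then keeps its data at the sites. A statistical analysis plan cannot repair this, because it cannot tabulate data that the protocol bars from central processing.

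At stake are the confirmatory test and the safety account of a post-market study. Time to release may look too short, and mortality and fatal related SAEs too rare. For hospital and ICU nights the direction is uncertain, because patients who die early also have short stays.

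**Working it through.** **1. The plan's own figure.** Section 6.3.7 gives 99 analysable patients, 80% power, two-sided 4.92%, a shape-1 Weibull (exponential) model, 3 months of follow-up and 13 expected events. A one-sample log-rank calculation returns 99 patients (power 80.1%) and 99 × (1 − 0.75^0.5) = 13.3 events, but only if 56% and 75% are entered as event-free proportions at 6 months. Enrolment is 99/0.90 = 110. Read as the protocol defines them, as proportions with stoma relocation, the same 99 patients give 99 × (1 − 0.25^0.5) = 49.5 events. That mismatch is a separate matter. Below, 56% is the proportion released at 6 months, as the text defines it.

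**2. Set-up under no benefit.** All treated patients together follow the control curve.
- Control hazard: λ0 = −ln(0.44)/6 = 0.1368 per month.
- A fraction q of treated patients is lost before consent, would not have been released, and has counterparts in the control data. The protocol gives no value for q.
- Release distribution among the enrolled: F0(t)/(1 − q), with F0(t) = 1 − exp(−λ0 t).
- Test: Z = (O − E)/√E, where E is the sum of λ0 × min(T, 3). False superiority means Z > 1.967.

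**3. Results** (n = 99, 3 months, 40,000 simulated studies per row):

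| q | Apparent release at 6 months, 0.56/(1 − q) | O/E | False superiority |
|---|---|---|---|
| 0 | 56.0% | 1.00 | about 3% |
| 1.8% | 57.0% | 1.02 | about 4% |
| 5% | 58.9% | 1.07 | about 7% |
| 6% | 59.6% | 1.08 | about 8% |
| 12% | 63.6% | 1.17 | about 18% |

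Hand check at q = 12%: expected releases are 99 × 0.3367/0.88 = 37.9, against E of about 32.3, a ratio of 1.17.

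**4. Where the values of q come from.** All deaths cited here are from section 3.2.
- 12% is the in-hospital EVT mortality (2 of 17) in a study of leaks after oesophagectomy.
- 6% halves that figure, because section 6.3 plans roughly equal upper and lower GI use. It assumes no loss in lower GI.
- 1.8% is 1/55. A cited study of 55 upper-GI patients had 4 deaths (7.2%), of which 3 followed complete healing.
- 5% is a round value in between.

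**5. A bound from counts alone.** A patient unreleased for the full 3 months adds 3 × 0.1368 = 0.41 expected events and no observed event. With q = 12%, 99 enrolled imply 99 × 0.12/0.88 = 13.5 lost patients, so E rises by 13.5 × 0.41 = 5.5, from about 32.3 to 37.9, which equals O. Adding the lost patients in this way returns the false-superiority rate to 2.5–3% for every q in the table.

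**The case against.** Several objections have force.

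- **The mortality figures are weak anchors.** Both are upper-GI and cover all or in-hospital deaths, not deaths before consent. A reader might infer that the cited 7.2% mortality translates directly into about 9% false superiority. The same source says that 3 of the 4 deaths followed complete healing, so treating all 7.2% as never released is unsupported. Healing is not identical to release, but only 1 of 55 is not described as healed.
- **The controls may share the omission.** The control in 6.3.7 is a published cohort summarised by a median and interquartile range. If it also omits early deaths, the tilt shrinks or vanishes. An unconditional claim that the comparison is biased towards the device is not supported.
- **The log is not the only measure.** Sections 6.4.8 and 8.1 provide pooled site details, 6.1.2 allows monitor review, and 6.5 allows visits after suspicious findings. It would be wrong to say there is no safeguard. None of these, however, is said to count deaths or incapacity before consent, and a visit triggered by checks on entered data is not prompted by patients who were never entered.
- **Eligibility timing.** Section 6.4.3 says that after signing, "patients are checked for eligibility according to in- and exclusion criteria". A reader might infer a second route for selection with hindsight. The documents give little support: 6.4.2 and 6.4.3 also describe a check on routine data at screening, and the criteria other than consent are baseline facts.
- **30-day mortality** is a recorded item, not a primary or secondary endpoint.
- **Analysis detail belongs in the SAP.** True of the sensitivity run, but not of the bar on the data, which only the protocol can lift.

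**Conclusion.** The point holds as a conflict between what the protocol relies on and what it permits. It creates selection between index use and consent, presents the screening form and log as the control, and then keeps the log from central use, with only potential local review. Treated patients lost before consent are missing from every endpoint and from the recorded 30-day mortality.

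The consequence is possible, not proven: the confirmatory comparison may favour the device, and mortality and fatal related SAEs may be understated. False superiority for a device with no benefit could be anywhere from close to the no-loss 3% to about 18% over losses of 0 to 12%. This holds only if the missing patients would not have been released and the controls include such patients. The 18% is an illustration at the top of that range, not an estimate for this study.

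**What to change.** 1. **Replace the sentence in 6.1.2** that bars central processing. Sites send anonymised aggregate counts of all treated but non-enrolled patients, split by upper and lower GI and by fixed reason codes that include died before consent and unable to consent. The counts are tabulated with the results. Section 6.1.1 already describes the screening data as anonymised, so aggregate counts raise no evident privacy obstacle.
2. **Present 30-day mortality and fatal SAEs together with the count of deaths before consent.**
3. **Add one bounding sensitivity run of the primary test.** Add the non-enrolled deaths, and in a worst case also the patients unable to consent, as not released, each with the full 3-month expected events (about 0.41 under the stated exponential control). Label it a conservative bound: counts carry no dates, and inability to consent is not failure to heal.

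No separate change to the timing of the eligibility check is needed. The cost is protocol wording, reason codes on an existing log, one table, one extra analysis and a small site effort to send counts. Clinical care and the consent process are unchanged. The counts show and bound the loss; they do not remove it.
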